It is well known that the use of alcohol is associated with an increased risk of hypoglycemia [5]. It is proposed that ethanol impairs gluconeogenesis. This might be due to alcohol dehydrogenase increasing NADH production. A decrease in NAD/ NADH ratio decreases pyruvate concentration, which is one of the primary paths to gluconeogenesis [5,6]. There is a higher risk of hypoglycemia when hepatic glycogen deposits are depleted (during the fasting state or food deprivation) because glycogenolysis then plays a reduced role in glucose level regulation [7]. There is a risk of hypoglycemia with large dose alcohol intake and even with occasional drinking and low blood alcohol level in those who have missed or delayed food intake [8].

There is a paucity of data on the effects of alcohol on glucagon effectiveness in patients with type 1 diabetes. However, it is known that alcohol intake increases the risk of hypoglycemia [9]. This might be due to multiple factors including: inhibition of gluconeogenesis, which has the main role in glucose production during hypoglycemia in patients with diabetes, impairment of rapid and slow glucose counter regulatory hormones including epinephrine, glucagon, cortisol and growth hormone and hypoglycemia unawareness because of the central effects of alcohol

Because some people with type 1 diabetes drink alcohol and because the bihormonal bionic pancreas uses glucagon for management, it is essential to determine whether alcohol will impair the effectiveness of glucagon and subsequently impair the effectiveness of the bihormonal bionic pancreas in preventing hypoglycemia.

I. b. Rationale and Potential Benefits

Alcohol reduces the production of glucose from the liver, mostly by reducing the rate of gluconeogenesis [6] Glucagon is thought to raise blood glucose primarily through glycogenolysis. Whether alcohol will reduce the ability of glucagon to prevent and treat hypoglycemia is not known. Since many people with diabetes drink alcohol, and because alcohol can reduce attentiveness to diabetes management, it is very important to know whether alcohol will impair the effectiveness of a bihormonal bionic pancreas in preventing hypoglycemia.

We will test the effectiveness of glucagon in raising blood sugar in the absence of ethanol and in the presence of defined blood alcohol content (BAC) levels in a random-order crossover design. An established alcohol infusion algorithm for a clamp study will be used (10). If there is a significant reduction in glucagon effectiveness in the presence of alcohol, this will be important information to give users. If glucagon remains equally effective in the presence of alcohol, this means that the bionic pancreas will provide an even larger margin of safety over usual care when people with type 1 diabetes chose to use alcohol because of the increased risk associated with the use of alcohol in usual care. Since the alcohol levels to be tested are relatively high, if there is no effect at these levels we can be confident that the lower alcohol levels associated with healthy consumption of alcohol (2 drinks a day or less) will have no effect on the effectiveness of the bihormonal bionic pancreas.

II. Hypothesis and Specific Aims

We hypothesize that a BAC of 0.1 will not significantly alter the anti-hypoglycemic effect of micro-dose glucagon.

The specific aim of this study is:

Aim 1. To quantify the effect of a blood alcohol content on the anti-hypoglycemic efficacy of glucagon using a hyperinsulinemic-normoglycemic clamp technique in volunteers with type 1 diabetes in a random-order crossover trial.

III. Subject Selection

III. a. Inclusion Criteria

- Age 21 to 80 years old with type 1 diabetes for at least one year.
- Diabetes managed using an insulin infusion pump using rapid-acting insulin such as insulin aspart (NovoLog), insulin lispro (Humalog), or insulin glulisine (Apidra) for at least one week prior to enrollment.
- Alcohol exposure on at least one occasion in the last year consisting of at least 4 drinks in one sitting.

III. b. Exclusion Criteria

- Unable to provide informed consent.
- Unable to comply with study procedures.
- Unable to refrain from the consumption of alcohol at least 24 hours prior to study start
- Current participation in another diabetes-related clinical trial that, in the judgment of the principle investigator, will compromise the results of the clamp study or the safety of the subject.
- Pregnancy (positive urine HCG), breast feeding, plan to become pregnant in the immediate future, or sexually active without use of contraception.
- Aldehyde dehydrogenase deficiency as determined by a screening questionnaire
- End stage renal disease on dialysis (hemodialysis or peritoneal dialysis).
- History of pheochromocytoma (because glucagon has been reported to precipitate hypertensive crisis in the setting of pheochromocytoma). Fractionated metanephrines will be tested in patients with a history increasing the risk for a catecholamine secreting tumor:
 - Paroxysms of tachycardia, pallor, or headache. Personal or family history of MEN 2A, MEN 2B, neurofibromatosis, or von Hippel-Lindau disease
 - Episodic or treatment of refractory (requiring 4 or more medications to achieve normotension) hypertension.
- History of adverse reaction to glucagon (including allergy) besides nausea, vomiting, or headache.
- Inadequate venous access as determined by study nurse or physician at time of screening.
- Liver failure or cirrhosis
- Hemoglobin < 12 gm/dl.
- History of problem drinking or alcoholism, regardless of whether active or in remission.
- Use of benzodiazepines or barbituates or opiates or other central nervous system depressant drugs that could act synergistically with ethanol to lower the level of consciousness
- Any other factors that, in the judgment of the principal investigator, would interfere with the safe completion of the study procedures.
- Use of medications that are known to cause QT interval prolongation (See Appendix A)

No volunteers will be excluded on the basis of gender or race. The requirement that volunteers manage their diabetes using subcutaneous insulin infusion pump therapy is imposed because multiple daily injection therapy involves the use of medium-acting basal insulin (such as NPH insulin) or long-acting insulin (such as glargine) that would either require an extended washout period or would result in unwanted variation in the GIR due to the pharmacokinetics of longer acting insulins. The requirement significant

ethanol use in the last year is to reduce the likelihood that the subject will experience an adverse reaction to the blood alcohol content levels that will be reached in the study. The exclusion of potential subjects with a history of alcoholism is to avoid the risk of relapse associated with ethanol exposure in the study.

III. c. Source of Subjects

Volunteers who fit the selection criteria will be considered as candidates for this study. Advertisements for the study will be posted at the MGH Diabetes Center and will be distributed in the weekly broadcast email of research studies seeking volunteers. We will post basic information about the trial along with contact information on our website www.artificialpancreas.org and the study will be posted on www.clinicaltrials.gov. We will also post information regarding the trial at online venues for people with type 1 diabetes, such as Glu (online community of the Type 1 Diabetes Exchange). We will also contact individuals who have previously inquired about participation in our studies and have asked us to have their contact information kept on file.

IV. Subject Enrollment

IV. a. Number of Subjects

It is expected that we will have 20 volunteers complete two full-length clamp experiments with 15 of those volunteer's using a consistent protocol. The experiments are expected to be completed over a time period of 4-6 months.

Up to 35 volunteers with type 1 diabetes will be enrolled. The upper bound is based on the expectation that some volunteers will be excluded after the screening visit and blood tests, the possibility that some qualified volunteers will not be able to complete an experiment for scheduling reasons, the possibility that some experiments may have to be discontinued before completion (e.g. due to inability to maintain IV access or subject withdrawal), and the likelihood that minor modifications to the protocol for adjustment of the GIR, alcohol infusion rate, or the insulin infusion rate may be required during the first 2-3 experiments.

IV. b. Enrollment Procedures

Prospective participants may be briefed by a study staff member by phone regarding the study procedure and the inclusion and exclusion criteria. Potential volunteers may be sent an informed consent document to review by email or post.

IV. c. Consent Procedures

Potential volunteers will meet with a study physician or nurse practitioner who will explain the study and answer questions. Informed consent will be administered by an MD or NP. In the event that a volunteer is a patient of one of the study MDs or NPs, another staff MD or NP will answer questions and administer consent. If a nurse practitioner is administering the consent, a physician will be available as back-up for additional support if needed and subjects will be offered the chance to speak with a study physician if they wish.

The study physician or nurse will also answer any questions that the volunteer may have during their participation. They will share any new information in a timely manner that may be relevant to the volunteer's willingness to continue participating in the trial. The volunteers may choose to discontinue their participation at any time.

Documentation of the informed consent process will be noted using the Documentation of Informed Consent Form in each volunteer's research record, including documentation of the option to speak with a study physician

V. Study Procedures

V. a. Screening data

- Age
- Sex
- Race and ethnicity
- Urine HCG for female volunteers
- Date of diabetes diagnosis
- Medical, surgical, and social history, allergies, and review of systems relevant to inclusion and exclusion criteria
- Subject's customary drinking history
- Date of last menstrual period in female volunteers
- Medications (prescription and non-prescription) and date of last change in medication regimen
- Duration of insulin pump use
- Insulin regimen (basal rate, sensitivity factor, and carbohydrate ratio)
- Average total daily dose of insulin in the last 30 days (from pump history)
- Height and weight
- Blood pressure
- Hemoglobin
- Fractionated metanephrines (in patients with history increasing the risk for a catecholamine secreting tumor)

V. b. Drugs

The study involves subcutaneous administration of *Eli Lilly glucagon*. Lilly glucagon is commercially available by prescription and is indicated for patients with type 1 diabetes.

The clamp procedure involves intravenous administration of *regular human insulin*, which is commercially available indicated for patients with type 1 diabetes. The insulin infusion includes 2% *human serum albumin*, which is added to the solution to prevent inactivation of insulin or loss of insulin on the walls of the administering syringe and IV tubing (10).

The clamp procedure also includes ethanol infusion solution (6 % v/v ethanol in ½ normal saline). Sterile pyrogen free IV ethanol 98% is diluted to 6 % v/v with ½ normal saline prior to use.

Intravenous infusion of *dextrose 20% solution* will also be administered.

Per MGH hypoglycemia procedures, one ampule of 50% dextrose will be given in the event of a hypoglycemic episode. Some side effects associated with taking dextrose include: dehydration, mental confusion, hyperglycemia and possible hyperosmolar syndrome which may result from too rapid administration.

In the event of any nausea, subjects will be given a small dose of ondansetron to alleviate symptoms of nausea. Ondansetron will only be administered upon the subject's request. Pain medications such as acetaminophen and ibuprofen will also be offered for pain and administered upon the subject's request. Adverse effects associated with taking acetaminophen include: rash, hives, redness of skin, itching, swelling of the face, throat, tongue, lips, eyes, hands, feet, ankles, or lower legs. Common side effects associated with taking ibuprofen include: nausea, vomiting, diarrhea, bloating and abdominal pain.

V. c. Devices

Ethanol clamp algorithm: Alcohol Infusion System Software. This is the software system, developed by the Indiana Alcohol Research Center ([name] [name]) that runs the PBPK (Physiologically Based

Pharmacokinetic) model, integrates breath alcohol measurements, computes the ethanol infusion rate profile to achieve the desired result, converts the profile into computer-controlled infusion pump instructions, runs the pump, and displays the results throughout the experiment (10, 11). The algorithm will be run on a laptop computer that will directly control the ethanol infusion pump.

Ethanol infusion pump: The Alaris Imed Gemini PC-2TX Infusion Pump is a computer controllable 2 channel pump that can be controlled by a computer using a serial connection.

Saline, and glucoseinfusion pumps: Standard hospital infusion pumps.

Breathalyzer: The handheld Alco-Sensor FST (Intoximeter, Inc) Breath alcohol analyzer will be used to measure Breath Alcohol Content (BrAC) at an accuracy of $\pm 0.005\%$ BAC at 0.100% BAC. Each subject will use a disposable mouth piece. A push on the ejection tab on the mouthpiece hygienically expels it from the Breathalyzer without any contact between the subject's saliva and the meter or the operator's hand. The meter will be professionally calibrated at least annually.

Intravenous catheters: Each volunteer will have two intravenous catheters introduced. One will be dedicated to withdrawal of samples and the other for infusion of insulin, ethanol and dextrose.

Nova Biomedical StatStrip Xpress Glucose Meter: The StatStrip Xpress glucose meter is FDA approved for outpatient and inpatient use and is commercially available. The meter will be cleaned between subjects according to the manufacturer's instruction.

HemoCue Hb 201 + Analyzer: The HemoCue is an FDA approved meter used to measure hemoglobin through blood obtained via finger stick.

Hot box: A hot box will use warm air to warm the forearm and hand of the subject in which the sampling IV catheter is placed for the purpose of arterializing venous blood.

V. d. Experimental Procedures and Data Collection

Screening Visit

- All volunteers will have a screening visit to confirm eligibility
- Female volunteers will have urine tested for HCG. If the test is positive, the volunteer will be informed of the result and the visit will be ended.
- The volunteer will be interviewed and the case report form will be completed by a study nurse or study physician to establish whether the volunteer is eligible to continue with the screening.
- A finger stick will be performed to test hemoglobin using the HemoCue Hb 201+ Analyzer. A blood draw will be performed in the event that the Hemocue measurement is out of range and, if indicated, plasma for metanephrines.
- A study physician or nurse practitioner will review the case report form and laboratory results to determine volunteer eligibility. If volunteers are not eligible to continue in the study, the results of abnormal tests will be reported to the volunteers and to a health care provider of their choosing.

Hyperinsulinemic-normoglycemic Clamp

We will test the effect of glucagon in the absence and presence of ethanol in a random-order crossover design. We will give each volunteer two identical injections of glucagon, one with a blood alcohol content of approximately 0 at one visit and another with a BAC of approximately 0.1 at another separate visit.

In Both Visits

- Subjects will report to the Clinical Research Center (CRC) by approximately 7:00 AM in the fasted state from 10pm the previous night. Subjects will be asked not to take any bolus insulin after 4 am, but to keep their basal insulin running.
- A urine HCG test will be performed for all female subject who are able to become pregnant. If the test is positive, the PI will inform the subject of the test result and the visit will be cancelled.

- A dipstick drug test will be performed to ensure that subjects are not under the influence of benzodiazepines or barbiturates or opiates that could synergize with ethanol to cause central nervous system depression.
- A Breathalyzer measurement will be obtained prior to the start of the visit to ensure the subject is not under the influence of alcohol.
- Two intravenous (IV) catheter lines will be placed, one in each arm. The sampling IV will be placed on the dorsal surface of the hand or the forearm. The catheters will typically be 20 gauge or smaller.
- Blood will be drawn for measurement of hemoglobin A1c, creatinine and estimated GFR, alanine aminotransferase (ALT), aspartate aminotransferase (AST), serum albumin, and free fatty acids.
- Regular human insulin will be added to the solution of 2% human serum albumin in normal saline to allow an infusion rate of 5-20 ml/hr based on the desired hourly insulin dose. Mixing of the insulin infusate will be performed by the research pharmacy and the final desired insulin concentration will be communicated to the research pharmacy in advance of the visit. The range of insulin concentrations in the infusate are expected to be from 0.2-1.2 u/ml, depending on the mean basal insulin rate of the subject.
- The subject will remove their own insulin pump and a primed continuous insulin infusion will be started using the insulin/saline/albumin mixture. The continuous rate will be between one-fold and four-fold higher than the mean basal insulin rate of the subject with the goal to use a minimum rate of 0.02 units/kg/hour. The insulin infusion may be used to give insulin boluses if the subject is hyperglycemic at arrival to reduce the time necessary to reach steady state. Once the appropriate rate is established (with a dextrose infusion rate that is neither too low nor too high), it will remain stable throughout the experiment. For a 70 kg, 5'10" tall man with a usual basal rate of 1 u/hr, an infusion at two-fold the usual basal rate would be 17 mU/m²/min. Therefore, for a 5 ml/hr infusion 19.88 units of insulin would be added to 50 ml of saline/albumin solution (~0.4 u/ml). A bolus of insulin that is three times the subject's mean basal rate will be given at the start of the clamp to accelerate the rise of insulin levels in the blood.
- An infusion of 20% dextrose in water will be started. BG values will be measured every 5 minutes using arterialized blood measured with the StatStrip Xpress. The dextrose infusion will be adjusted so that the blood glucose is stabilized at 90 ± 5 mg/dl. If the dextrose infusion rate is less than 2 mg/kg/min or greater than 8 mg/kg/min (for the 70 kg, 5'10" tall man, 42-168 ml/hr) then the insulin infusion rate may be adjusted. Initial stabilization is expected to take less than 3 hours.
- Blood samples (5ml) will be processed for plasma for later insulin and glucagon measurement every 20 minutes throughout the experiment.

During the Ethanol Infusion Visit Only

- Once the insulin infusion rate is established and the dextrose infusion rate has been stable for 15-20 minutes with the BG in the target range, the ethanol infusion will be started.
- The ethanol loading dose will be infused over 30 minutes, followed by a maintenance infusion. The target BAC is achieved by a specific dose and rate of alcohol infusion that is computed for each subject by estimating physiological parameters that include subject's alcohol elimination rate. An established computer model will be used (10) which is physiologically based on alcohol pharmacokinetic modeling. The parameters are based on height, weight and gender.
- We will use a breathalyzer to estimate BAC and will adjust the maintenance infusion accordingly to reach and maintain a BAC of 0.1 ± 0.01 . This is expected to take 30 to 45 minutes. Breathalyzer readings will be collected every 5 minutes until the BAC of 0.1 is reached, and then the levels will be checked every 10 minutes.
- The ethanol infusion will be continued for a maximum of up to 4 hours
- A mock ethanol infusion will be delivered during the non ethanol visits, consisting of the half-normal saline vehicle that the ethanol is normally delivered in. This will be done in order to keep the total amount of fluid infused the same. This will be started at approximately the same time, when the insulin infusion rate has been established and the dextrose infusion rate has been stable for 15-20 minutes. The computer model will run a standard profile based on the subject's height, weight and gender without any BAC measurements needed. When the computer model predicts that the BAC has reached the desired value, and the GIR remains stable for 15-20 minutes, the

injection will be given. Note that BAC measurements in the ethanol visits will modify the standard profile to achieve a true BAC of 0.1%, but the deviations from the standard profile are usually not large, so that the volume of half-normal saline delivered will be approximately the same during ethanol and non-ethanol visits.

•
In Both Visits

- Once the GIR has been stable for 15-20 min (and the BAC has been stable at 0.1 ± 0.01 for at least 10 minutes in the Ethanol Infusion Visit or the predicted BAC has been stable for at least 10 minutes in the non-ethanol visits) two baseline plasma samples will be obtained 5 minutes apart and the glucagon injection will be given.
- A bolus of 50 mcg of Lillyglucagon will be administered by subcutaneous injection using a syringe and a small gauge needle at a depth of less than 1 cm.
- In the 60 minute period after the glucagon injection, the frequency of BG checks will be increased to every 2 minutes and blood samples will be processed for plasma at every other check (every 4 minutes).

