- Height and weight
- Blood pressure
- Hemoglobin A1c
- Hemoglobin
- Creatinine and estimated GFR
- Serum Albumin
- Aspartate aminotransferase (AST)
- Alanine aminotransferase (ALT)
- Fractionated metanephrines (in subjects with history increasing the risk for a catecholamine secreting tumor)
- Free fatty acids

During the hyperinsulinemic-normoglycemic clamp:

- Venous BG measurements
- Timing and size of glucagon dose
- Insulin infusion rate
- Glucose infusion rates

- Ethanol infusion rate
- BAC according to breath alcohol meter
- BAC according to blood alcohol measurement
- Plasma insulin levels during the hyperinsulinemic-normoglycemic clamp
- Plasma glucagon levels during the hyperinsulinemic-normoglycemic clamp
- Any adverse events

VI. b. Study Endpoints

Primary endpoint analysis:

- Area over the curve for the glucose infusion rate in the hour following a subcutaneous glucagon dose (AOC_{GIR}) with a blood alcohol content of 0 vs. approximately 0.1%

Secondary endpoint analyses:

- Maximum change in GIR from baseline after glucagon injection in the presence and absence of ethanol

We will calculate means, median, percentages, standard deviations, standard errors, inter-quartile ranges, and 95% confidence intervals in descriptive analyses. We will use paired t-test for comparison of means. We will use multivariate regression models with repeated measurements to compare means and percentages while adjusting for patient demographics characteristics such as age, gender, body mass index, and body surface area.

VI. c. Power Analysis

Assuming that the standard deviation in each arm is 20% of the mean, and a within-patient correlation of 0.5, a sample size of 15 achieves 95% power to detect equivalence when the margin of equivalence is from -20% to 20% assuming the actual mean difference is zero. The significance level (α) is 0.05 using two one-sided paired t-tests. These results are based on 2000 Monte Carlo samples.

VII. Risks and Discomforts

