The study will be conducted by the staff of the MGH Diabetes Research Center (DRC) in cooperation with the staff of the CRC. The PI will conduct meetings with study staff at least twice a month to review study progress, discuss any issues in study conduct, and review procedures. Study staff will be encouraged to raise any concerns they may have or problems they have identified at these meetings. The PI will decide a course of corrective action, and resolution or progress will be assessed no later than the next bimonthly meeting. An audit of procedures, regulatory documentation, and a sample of volunteer files will be performed by a member of the DRC at least biannually. The audit will be conducted by a DRC staff member not directly involved in the conduct of the study. This audit will include a review of regulatory documentation, such as IRB correspondence, and a review of files, including a review of consents, case report forms, and other data from study visits.

A numeric code will be substituted for the volunteers personal identifying information in the study database, which will be password protected. The key linking the medical record number of the volunteer with the numeric code, along with case report forms, and all information that is personally identifiable, will be kept in a locked filing cabinet in an investigator's locked office. All electronic records will be kept in a password protected computer database. All printed computer data will be disposed of confidentially when no longer needed. Only the study staff will have access to the study database. Subjects may not withdraw

from the de-identified database, but they may elect to have the key linking their medical record to the de-identified database destroyed.

The study data may be shared with collaborators outside of Partners, but only in a form in which all personally identifiable information has been removed. Shared data will be in the form of a database in which only a number identifies volunteers.

IX. b. Safety Monitoring

A study physician or nurse practitioner will directly supervise each experiment. The PI will be informed of any adverse events immediately and will make any adjustments to the study protocol as needed to maintain subject safety.

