The Research Pharmacy will mix the insulin and ethanol solution. The calculations for the insulin infusion rate and the mixing of the insulin solution will be done in advance and checked by another physician or nurse practitioner. The calculations for the alcohol infusion rate will be done in advance and checked by another physician or nurse practitioner.

This study will be conducted under an Investigational New Drug application sponsored by the PI.

This study is considered moderate risk. The Principal Investigator and co-investigators will evaluate each experiment. Unanticipated problems, including adverse events, will be reported to the Partner's IRB in accordance with the PHRC policy on Unanticipated Problems Involving Risks to Subjects or Others including adverse events. An external Data and Safety Monitoring Board will oversee the conduct of the study and review its results on a regular basis. Additionally, the DSMB will be informed after any experiment that has to be discontinued due to hypoglycemia, hyperglycemia, or any unexpected adverse event. DSMB review will occur before any further experiments are performed. The DSMB will be informed if there are any changes to the study protocol that could significantly impact the safety or scientific validity of the study. A final DSMB meeting will convene after the completion of the study. After the first DSMB meeting, subsequent meetings may be convened via e-mail or conference call. Safety and efficacy data will also be reported to the FDA in compliance with applicable regulations.

IX. c. Adverse Event Reporting Guidelines

The PI will review any adverse events after each experiment. Adverse events will be reported to the Partner's IRB, the DSMB, and to the FDA.

X. Subject Compensation

Financial compensation of \$50 will be provided to all subjects who complete a screening visit. Subjects will be compensated \$200 after completion of each visit for a total of \$450 for the entire study.

XI. References

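### Does it matter that the plan does not say whether the 15 consistent-protocol completers or all 20 completers are the primary analysis set?

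*Combined protocol and SAP*

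**What the plan says.** Section IV.a (Number of Subjects) forecasts "20 volunteers complete two full-length clamp experiments with 15 of those" volunteers "using a consistent protocol", within an enrolment cap of 35. Among its reasons for the cap it lists "minor modifications to the protocol for adjustment of the GIR", the alcohol infusion rate or the insulin infusion rate, and it places these changes in the first two or three experiments.

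Section VI.b gives the primary endpoint as "Area over the curve for the glucose infusion rate in the hour following a subcutaneous glucagon dose", compared between blood alcohol of 0 and about 0.1%. On method it says "We will use paired t-test for comparison of means" and adds regression models. It does not say which completers enter.

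Section VI.c states that "a sample size of 15 achieves 95% power to detect equivalence" with a margin of ±20%, using two one-sided paired t-tests (TOST) at 0.05.

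Section IX.b, on safety, says of the investigators that "The Principal Investigator and co-investigators will evaluate each experiment" and of the principal investigator that he or she "will make any adjustments to the study protocol as needed to maintain subject safety".

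**The concern.** The plan describes two nested groups and assigns neither to the primary analysis. Three features make this look worse than a missing line.

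- The boundary cannot be rebuilt from the text. Twenty minus 15 leaves five completers outside the consistent group, yet changes are expected only in the first two or three experiments. With two experiments per volunteer, that could be as few as one or two people.
- One of the expected modifications concerns how the glucose infusion rate (GIR) is adjusted, and the primary endpoint is computed from the GIR.
- The staff who would judge when the procedure had settled watch the GIR during each clamp.

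If the set were settled after results were known, a reassuring claim that alcohol does not impair glucagon could rest on a favourable choice, and the chance of wrongly declaring equivalence would exceed 5%.

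**Working it through.** **Inputs, all from VI.c and IV.a.** SD in each arm 20% of the mean; within-patient correlation 0.5; margin ±20%; TOST at 0.05 per side; 15 or 20 pairs.

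**SD of the paired difference.** √(20² + 20² − 2 × 0.5 × 20 × 20) = √400 = 20%.

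**The plan's own figure.** Exact TOST power, integrating over the distribution of the sample SD, is 95.8% for 15 pairs at zero difference. This agrees with the stated 95%. For 20 pairs it is 99.2%.

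**How far apart the two tests are.** TOST passes when the 90% confidence interval lies inside ±20%. Taking the sample SD as 20%:

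- 15 pairs: half-width 1.761 × 20/√15 = 9.1, so the observed mean difference must lie within ±10.9%.
- 20 pairs: half-width 1.729 × 20/√20 = 7.7, so it must lie within ±12.3%.

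The thresholds differ by about 1.4 points. Disagreement should therefore be rare near zero and most common when the true loss lies near 11-12%.

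**Disagreement between all 20 and the last 15** (simulation, 200,000 trials per row, one common mean and SD):

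| True loss | Disagree | 20 pass, 15 fail | 15 pass, 20 fail |
|---|---|---|---|
| 0% | 3.7% | 3.6% | 0.2% |
| 5% | 9.6% | 8.7% | 0.9% |
| 10% | 18.8% | 15.3% | 3.5% |
| 12% | 19.2% | 14.5% | 4.7% |
| 15% | 14.8% | 10.0% | 4.8% |
| 20% | 4.3% | 2.1% | 2.1% |

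At a 10% loss, power is 69.5% with 20 pairs and 57.8% with 15. The gap of 11.7 points is the difference between the last two columns (15.3 − 3.5 = 11.8, equal within simulation error). It would be there however carefully the set had been named. A disagreement here means equivalence shown against not shown; it does not mean equivalence against a demonstrated loss. With the two-sided paired t-test of VI.b the pattern is similar: about 5% disagreement at zero loss and a maximum of about 20% near a 10% loss.

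**If only the first two or three volunteers are set aside** (18 or 17 pairs against 20), the maximum is about 11% or 14%.

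**False equivalence at a true loss of exactly 20%:**

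- Either set fixed in advance: 5.0%.
- Better of two sets, chosen after results: 6.3% (20 or 18), 6.6% (20 or 17), 7.1% (20 or 15).
- Best enrolment-order cut-off, chosen after results: 7.3% (dropping the first 0-3), 8.6% (dropping the first 0-5).

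**If the early pairs behave differently (assumed values).** If the five early pairs have an SD of 40%, disagreement at a 10% loss is 28%. If their mean effect differs by 20 points, it is about 8% when the true loss in the 15 is zero and about 35% when it is 10%. In those cases the 15 consistent pairs are the natural set to rely on, and they are the set VI.c is sized for.

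**The case for a change.** The strongest reply is that matching numbers are not a rule. VI.c sizes the trial and does not say who is analysed. Even if the 15 are meant, nobody can tell from the text which volunteers they are, and the people drawing the line can see the outcome variable as it accrues. Notifying the monitoring board of protocol changes does not settle an analysis set. A short definition would cost almost nothing.

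Part of this stands. The definition is missing, and the step from two or three experiments to five volunteers is unexplained. A sentence naming the primary set before GIR outcomes are analysed would be good housekeeping.

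The rest is weaker. The passages on evaluating each experiment and adjusting the protocol come from the safety section; the adjustments are tied to subject safety, and neither passage concerns who is analysed. Seeing the GIR during the experiment is inherent in a clamp and does not show that membership depends on the computed endpoint. The expected changes are placed at start-up, so a boundary by enrolment order is the ordinary reading. The inflated error rates describe a choice made after the results, and nothing in the plan provides for one.

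**Conclusion.** The concern does not require a change. It identifies missing detail that analysts would fill sensibly: the 15 consistent-protocol pairs as primary, in line with VI.c, and all completers as a supporting analysis. No stated rule gives a wrong result, and either set fixed in advance is a valid 5% test.

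Under the plan's SD, correlation and margin, with all pairs sharing one mean and SD, the choice alters whether equivalence is shown in about 1 trial in 27 at the planned zero difference. It does so in at most about 1 in 5, and that needs a true loss of 10-12%. Most of this is the ordinary power advantage of the larger set. The only damage to error control is a rise from 5% to about 6-9%, and it depends on selection after results that the plan does not call for. The disagreement rates would be higher if the early pairs were noisier or had a different mean effect. They would also be higher if the SD of the difference exceeded 20%: at an assumed 30% the two sets disagree in 26% of trials at zero difference. That is a question about the planning SD, which naming the set would not settle.
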